9.12.7 Treadmill Exercise

Participants will determine their max heart rate (HR) in the clinic at visit 1 (screening, Day 0) via graded treadmill test with a chest strap heart rate monitor (Section 9.12.6). Eligible participants will return and exercise on the treadmill at visit 2 (period 1, Day 1), visit 5 (period 1, Day 8), visit 6 (period 2, Day 1), and visit 9 (period 2, Day 8). On the day of the exercise, participants will be instructed to warm up on the treadmill first for five minutes at a leisurely walking pace. When the participants are ready, speed will be increased to 60% of participant's HRmax with 5% grade incline and they will be instructed to walk on the treadmill for 30 minutes or until exhaustion (11).

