1.8 Study Design, Visit Breakdown and Schedule of Assessment

This is a randomized, double-blind, comparator-controlled, crossover study to evaluate safety and efficacy conducted at Prism Clinical Research Clinic, Saint Paul, MN, USA, a KGK Science Inc. partner.

A total of 18 participants were enrolled in the study. The allocation of participants is provided in **Table 1**. The schedule of visits is presented in **Figure 1**. The schedule of assessments is described in **Table 2**.

A randomized, double-blind, comparator-controlled, cross-over study to investigate the safety and efficacy of RiaGev™ in healthy adults

Table 1. Allocation of participants

Study Arm	Number of Participants
RiaGev™ → Comparator	N = 9
Comparator → RiaGev™	N = 9
Total	N = 18

Figure 1. Study design

[figure not shown]

Table 2. The schedule of assessments

Procedures/assessments	Visit 1 Screen	Visit 2 Day 1 (+1 Day)	Visit 3 Day 3 (+1 Day)	Visit 4 Day 5 (+1 Day)	Visit 5 Day 8 (+1 Day)	Visit 6 Day 1 (+1 Day)	Visit 7 Day 3 (+1 Day)	Visit 8 Day 5 (+1 Day)	Visit 9 Day 8 (+1 Day)
Informed consent	X								
Review inclusion/exclusion criteria	X	X							
Review medical history	X								
Review concomitant therapies	X	X	X	X	X	X	X	X	X
Vitals: Height*, weight, heart rate, blood pressure *Height will only be measured at Visit 1	X	X	X	X	X	X	X	X	X
Urine pregnancy test	X	X							
Electrocardiogram (EKG)	x								
Physical examination	X	X							X

A randomized, double-blind, comparator-controlled, cross-over study to investigate the safety and efficacy of RiaGev™ in healthy adults

Procedures/assessments	Visit 1 Screen	Visit 2 Day 1 (+1 Day)	Visit 3 Day 3 (+1 Day)	Visit 4 Day 5 (+1 Day)	Visit 5 Day 8 (+1 Day)	Visit 6 Day 1 (+1 Day)	Visit 7 Day 3 (+1 Day)	Visit 8 Day 5 (+1 Day)	Visit 9 Day 8 (+1 Day)
Randomization		X							
CBC, electrolytes (Na, K, Cl), HbA1c*, fasting glucose, eGFR, creatinine, AST, ALT, and total bilirubin *HbA1c will only be measured at Visit 1	X				X	X			X
Maximum heart rate (HR _{max}) treadmill test	X								
Skin fluoroscopy for NADH analysis (optional)		X			X	X			X
Blood Collection for NAD+ analysis		X	X	X	X	X	X	X	X
Blood Collection for GSH/GSSG and ATP/AMP analyses		X			X	X			X
OGTT: glucose and insulin T= 0, 15m, 30m, 45m, 60m, 90m, 2h		X			X	X			X
Questionnaire		X	X	X	X	X	X	X	X
Treadmill Exercise protocol		X			X	X			X
Salivary Collection Kit Dispensed	X	X	X	X	X	X	X	X	
Salivary Collection Kit Returned		X	X	X	X	X	X	X	X

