2.2 Effectiveness/Efficacy analysis

2.2.1 Primary Outcome:

The primary outcome is the change in whole blood NAD⁺ levels from baseline to day 8 when supplemented with RiaGev™ or comparator.

The primary null hypothesis is as follows:

H₀: There is no significant difference in mean change in NAD⁺ level from pre-supplementation to post-supplementation, between subjects taking RiaGev™ or comparator.

Possible differences before exercise from day 1 to days 3, 5 and 8 between the study groups will be assessed using repeated-measures mixed ANCOVA. The model will include treatment, visit number, sequence and period as fixed effects and subject as a random effect. Between group p-values will be obtained from this model, while within group p-values will be obtained using paired t tests or Wilcoxon Signed Rank test as appropriate.

Possible differences at after exercise from day 1 to day 8 between the study groups will be assessed using repeated-measures mixed ANCOVA. The model will include treatment, visit number, sequence and period as fixed effects and subject as a random effect. Between group p-values will be obtained from this model, while within group p-values will be obtained using paired t tests or Wilcoxon Signed Rank test as appropriate.

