Assessment of the change in the level of salivary cortisol from day 1 to days 3, 5 and 8 will be conducted using repeated-measures mixed ANCOVA. The model will include treatment, visit number, sequence and period as fixed effects and subject as the random effect. Between group p-values will be obtained from this model, while within group p-values will be obtained using paired t tests or Wilcoxon Signed Rank test as appropriate.

5. The change in Checklist Individual Strength (CIS) Questionnaire outcome after a 7-day supplementation with either RiaGev™ or comparator

The domains for this questionnaire are:

1. Subjective feeling of fatigue: sum of the scores for items 1, 4, 6, 9, 12, 14, 16, and 20
2. Concentration: sum of the scores for items 3, 8, 11, 13, and 19
3. Motivation: sum of the scores for items 2, 5, 15, and 18
4. Physical activity: sum of the scores for items 7, 10, and 17
5. Total: sum of the scores for the four sub-scales listed above

For item 2, 5, 6, 7, 8, 11, 12, 15, and 20, the score is 1 for “yes, that is true” and 7 for “no, that is not true”. For item 1, 3, 4, 9, 10, 13, 14, 16, 17, 18, and 19, the score is 7 for “yes, that is true” and 1 for “no, that is not true”.

Assessment of change in each CIS domain will be conducted using repeated-measures mixed ANCOVA. The model will include treatment, visit number, sequence and period as fixed effects and subject as the random effect. Between group p-values will be obtained from this model, while within group p-values will be obtained using paired t tests or Wilcoxon Signed Rank test as appropriate.

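### The NAD+, cortisol and CIS models list visit number beside period, which it determines, and contain no Day 8 treatment contrast although the primary endpoint is the change to Day 8

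*SAP*

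**What the plan says.** SAP 2.2.1 defines the endpoint: "The primary outcome is the change in whole blood NAD⁺ levels from baseline to day 8". It then gives two repeated-measures mixed ANCOVA models. The first covers "Possible differences before exercise from day 1 to days 3, 5 and 8 between the study groups", the second "Possible differences at after exercise from day 1 to day 8 between the study groups". Both carry the same model statement: "The model will include treatment, visit number, sequence and period as fixed effects and subject as a random effect". SAP 2.2.2 repeats it for salivary cortisol (outcome 4) and the CIS domains (outcome 5): "The model will include treatment, visit number, sequence and period as fixed effects and subject as the random effect". In all four places the between-group p-value is to come from the stated model, and no interaction term is listed.

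Visit number is not defined in the statistical sections. The visit schedule (SAP 1.8, Table 2; Protocol 1.3) numbers visits 1 to 9 across the whole study, and Protocol 9.12.7 ties those numbers to periods: "visit 5 (period 1, Day 8), visit 6 (period 2, Day 1), and visit 9 (period 2, Day 8". Day 8 is thus "Visit 5 Day 8 (+1 Day") in one column of SAP Table 2 and "Visit 9 Day 8 (+1 Day") in another.

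The GSH/GSSG and ATP/AMP models, which also run from Day 1 to Day 8, omit visit number.

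**The concern.** There are two linked problems. First, if no visit number occurs in both periods, a visit factor already contains period. The analyst must then choose a term to drop or a recoding, and for the primary model the SAP leaves that choice open. SAP 2.1 names R but no routine or coding.

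Second, the model has no parameter for the treatment difference at Day 8. Day 8 is two separate levels of the visit factor, and treatment enters only as a main effect, so its p-value refers to an average over the modelled days. At stake is whether the primary p-value tests the primary endpoint.

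**Working it through.** **Inputs.** There are 18 participants, 9 per sequence (Protocol 6; SAP Table 1). Post-baseline Days 3, 5 and 8 are Visits 3, 4, 5 in period 1 and 7, 8, 9 in period 2. The fixed effects are those in SAP 2.2.1. A Day 1 baseline covariate is implied by ANCOVA and named in Protocol 11.3. The documents give no figure of their own for this point, so there is none to reproduce.

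**Step 1: columns and rank.** Intercept 1 + treatment 1 + visit 5 (six levels less one) + sequence 1 + period 1 = 9 columns. The period 2 indicator equals the sum of the indicators for Visits 7, 8 and 9, so one column is redundant and the rank is 8. A baseline covariate makes this 10 columns, rank 9.

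**Step 2: other codings, by design matrix.**

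| Model | Columns | Rank | Period estimable | Treatment estimable |
|---|---|---|---|---|
| Days 3/5/8, visit as factor + period, baseline covariate | 10 | 9 | no | yes |
| Same, Day 1 kept as a response instead of covariate | 11 | 10 | no | yes |
| Days 3/5/8, visit as a number + period, baseline covariate | 6 | 6 | yes | yes |
| Days 3/5/8, day as factor + period, baseline covariate | 7 | 7 | yes | yes |
| Same, plus treatment-by-day | 9 | 9 | yes | yes |
| After exercise, Day 8 only, baseline covariate, visit as factor or number + period | 6 | 5 | no | yes |

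Numeric visit restores full rank in the Days 3/5/8 model, but only by imposing a straight line over Visits 3 to 9. In the after-exercise model with Day 8 values only, the visits are 5 and 9, so visit number and period are the same variable in either coding.

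**Step 3: effect on the treatment term.** In one simulated complete data set the least-squares treatment coefficient was 0.8163 with visit plus period (redundancy resolved), with visit alone, and with day plus period. The first two models span the same space. The third differs only by day-by-period terms, which are orthogonal to treatment when the data are complete.

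**Step 4: what that term estimates.** With treatment as a main effect and complete data, the coefficient is (d3 + d5 + d8)/3, where d is the treatment difference on that day. The documents do not give the time course. As an assumption, let the Day 3 and Day 5 differences each be a fraction f of the Day 8 difference, and set d8 to 8.7, the difference in Protocol 11.1. The average is 8.7 × (1 + 2f)/3:
- f = 1: 8.7
- f = 0.5: 5.8
- f = 0: 2.9

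If the early difference were larger than at Day 8 (f above 1), the average would exceed the Day 8 value.

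**Step 5: precision of a Day 8 contrast.** Suppose within-person treatment differences have equal variance on each day and correlation r between days. The variance of the three-day average is then (1 + 2r)/3 times that of one day, so the Day 8 standard error is √(3/(1 + 2r)) times as large. For assumed r of 0.8, 0.5 and 0 this is √(3/2.6) = 1.07, √(3/2) = 1.22 and √3 = 1.73. The stated model, with subject as its only random effect, treats these differences as uncorrelated, which is the 1.73 end.

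**The case against.** The best defence is that visit number was meant as the visit within a period. The preceding sentence in SAP 2.2.1 sets the time axis by day, and listing period separately is natural on that reading. The Days 3/5/8 models are then of full rank. This stands as a possible intention, so the rank deficiency is conditional on coding. But the SAP says so nowhere, and the only numbering printed is 1 to 9. The reading also does not rescue the after-exercise model: with Day 8 values only, day within period is a constant. Nor does it supply a Day 8 contrast.

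A second defence is that period is a nuisance term which the visit levels absorb. That is correct for the averaged treatment effect (step 3).

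A reader might infer two stronger things that the documents do not support.
- *That the primary model cannot be fitted or treatment cannot be tested.* Treatment is estimable under every coding in step 2. What cannot be estimated separately is period or one visit level.
- *That within-person precision is lost.* A contrast at one visit number would compare 9 people with 9 others, with a standard error √(2/(1 − ρ)) times that of the crossover Day 8 contrast (2.0 at ρ = 0.5 and 2.6 at 0.7, assumed within-person correlations). The SAP specifies no such contrast. Its treatment term uses both periods of each person, and averaging the contrasts at Visits 5 and 9 would return the crossover Day 8 estimate.

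**Conclusion.** The point holds as a specification fault in four model statements, including the primary one. On the documents' own numbering, with visit as a factor, the listed fixed effects exceed the rank by one. The averaged treatment effect survives, unchanged if data are complete; step 3 does not cover incomplete data. The weightier part does not depend on coding: without a treatment-by-day term the Days 3/5/8 model tests an average over those days, not the stated change to Day 8. How far the two differ depends on a time course that the documents do not give; in the step 4 illustration the average ranges from one third of the Day 8 difference to all of it. The change should be made, but the fault does not invalidate the treatment comparison.

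**What to change.** 1. In the Days 3/5/8 NAD+ model (SAP 2.2.1, first paragraph) and in the cortisol and CIS models (2.2.2, outcomes 4 and 5), replace visit number with study day within period (3, 5, 8) as a categorical term. Keep period and add treatment-by-day. State that the Day 1 value of each period is the covariate.
2. Name the Day 8 treatment contrast as the primary test for NAD+, or fit a Day 8-only model. Changing visit to day without the interaction would restore full rank but still test the average.
3. In the after-exercise paragraph, delete visit number and model the Day 8 value with baseline as covariate. This matches the terms already listed for GSH/GSSG and ATP/AMP.

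The cost is four edited model statements and no new data. The Day 8 contrast has a larger standard error than the three-day average: slightly larger if a person's treatment differences are highly correlated across days, and up to 1.73 times if they are uncorrelated (step 5). That is the price of testing the endpoint as defined. It does not undercut the planned size if the SD of 11.04 in Protocol 11.1 is that of a single within-person difference: on that assumption a two-sided paired t-test at 5% needs 15 completers for 8.7 (power 0.81), and 15 × 1.2 = 18.

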2.2.2 Secondary Outcomes

1. The change in serum glucose and insulin as assessed by an Oral Glucose Tolerance Test (OGTT) at t=0, 15m, 30, 45m, 60m, 90m and 2h after a 7-day supplementation with either RiaGev™ or comparator.

The change in serum glucose and insulin will be represented as change in mean concentrations at each time point. Assessment of change in mean concentrations for each analyte will be conducted using repeated-measures mixed ANOVA. The model will include treatment, time, sequence and period as fixed effects and subject as the random effect. Between group p-values will be obtained from this model, while within group p-values (from day 1 to day 8) will be obtained using paired t tests or Wilcoxon Signed Rank test as appropriate. An incremental area under the curve (iAUC) will be calculated for each group and compared between groups using mixed ANOVA, with study group, sequence and period as fixed effects and subject as the random effect.

2. The change in serum Glutathione/Glutathione disulfide (GSH/GSSG) ratio after a 7-day supplementation with either RiaGev™ or comparator

Assessment of the change in the ratio from day 1 to day 8 will be conducted using repeated-measures mixed ANCOVA. The model will include treatment, sequence and period as fixed effects and subject as the random effect. Between group p-values will be obtained from this model, while within group p-values will be obtained using paired t tests or Wilcoxon Signed Rank test as appropriate.

3. The change in serum adenosine triphosphate/ adenosine monophosphate (ATP/AMP) ratio after a 7-day supplementation with either RiaGev™ or comparator

Assessment of the change in the ratio from day 1 to day 8 will be conducted using repeated-measures mixed ANCOVA. The model will include treatment, sequence and period as fixed effects and subject as a random effect. Between group p-values will be obtained from this model, while within group p-values will be obtained using paired t tests or Wilcoxon Signed Rank test as appropriate.

4. The change in salivary cortisol after a 7-day supplementation with either RiaGev™ or comparator

Assessment of the change in the level of salivary cortisol from day 1 to days 3, 5 and 8 will be conducted using repeated-measures mixed ANCOVA. The model will include treatment, visit number, sequence and period as fixed effects and subject as the random effect. Between group p-values will be obtained from this model, while within group p-values will be obtained using paired t tests or Wilcoxon Signed Rank test as appropriate.

5. The change in Checklist Individual Strength (CIS) Questionnaire outcome after a 7-day supplementation with either RiaGev™ or comparator

The domains for this questionnaire are:

1. Subjective feeling of fatigue: sum of the scores for items 1, 4, 6, 9, 12, 14, 16, and 20
2. Concentration: sum of the scores for items 3, 8, 11, 13, and 19
3. Motivation: sum of the scores for items 2, 5, 15, and 18
4. Physical activity: sum of the scores for items 7, 10, and 17
5. Total: sum of the scores for the four sub-scales listed above

For item 2, 5, 6, 7, 8, 11, 12, 15, and 20, the score is 1 for “yes, that is true” and 7 for “no, that is not true”. For item 1, 3, 4, 9, 10, 13, 14, 16, 17, 18, and 19, the score is 7 for “yes, that is true” and 1 for “no, that is not true”.

Assessment of change in each CIS domain will be conducted using repeated-measures mixed ANCOVA. The model will include treatment, visit number, sequence and period as fixed effects and subject as the random effect. Between group p-values will be obtained from this model, while within group p-values will be obtained using paired t tests or Wilcoxon Signed Rank test as appropriate.

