11.3 Statistical Analysis Plan

The primary outcome is the change in whole blood NAD+ levels from baseline to day 6 compared between $RiaGev^{TM}$ and comparator.

An effectiveness analysis based on the intent-to-treat population and an efficacy analysis based on the per protocol population will be performed. Safety analysis will be done for the safety population.

Variables will be tested for normality and transformed to the log scale if found to be non-normally distributed. Log-normally distributed variables will be analyzed in the logarithmic domain. Intractably non-normal outcome variables will be analyzed by appropriate non-parametric tests.

Missing values in the intent-to-treat and per protocol analyses will be imputed using the most recent previously-available value (LOCF, or "last-observation-carried-forward" imputation) or multiple imputation methods. No imputation will be performed for missing safety values.

For each continuous endpoint, a summary table will be prepared with a variety of summary statistics including mean, standard deviation, median and range values for each time point-treatment pairing. To account for any a priori differences between groups, the summary statistics of the changes from baseline will also be provided. For parameters requiring a logarithmic transformation, the summary statistics will be provided as non-transformed values. Mean values will be displayed as graphs, with a separate line for each product, and error bars indicating standard errors or standard deviations. Mean changes from baseline will be graphed similarly. Although imputed data will be used for significance testing, non-imputed data will be used for presenting summaries. Categorical variables will be summarized as counts and percentages.

Continuous efficacy endpoints will be tested for significance between groups by Analysis of Covariance (ANCOVA). The dependent variable will be the measurement at each visit, the factor will be the treatment group, and the value at baseline (Day 1) will be the covariate. A within group analysis on effectiveness/efficacy endpoints will be done using the Student's paired t-test or, in the case of intractable non-normality, the Wilcoxon sign rank test. Categorical variables will be compared using Chi-squared or Fisher's Exact tests as appropriate.

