1.4 Secondary Outcomes

1. The change in serum glucose and insulin as assessed by an Oral Glucose Tolerance Test (OGTT) at t=0, 15m, 30, 45m, 60m, 90m and 2h after a 7-day supplementation with either RiaGev™ or comparator.
2. The change in serum Glutathione/Glutathione disulfide (GSH/GSSG) ratio after a 7-day supplementation with either RiaGev™ or comparator
3. The change in serum adenosine triphosphate/ adenosine monophosphate (ATP/AMP) ratio after a 7-day supplementation with either RiaGev™ or comparator
4. The change in salivary cortisol after a 7-day supplementation with either RiaGev™ or comparator
5. The change in Checklist Individual Strength (CIS) Questionnaire outcome after a 7-day supplementation with either RiaGev™ or comparator.

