2.1 General Approach

The primary and secondary endpoints will be analysed for both ITT and PP population. Safety parameters will be analysed for Safety population. All data will be summarised by study group, visit and/or study week as specified in the study objectives.

For nominal variables, counts and percentages will be presented. The denominator for each percentage will be the number of participants within the study group at that visit unless otherwise specified.

For interval variables, the arithmetic mean, standard deviation, median and min-max range will be presented to two decimal places. This will be accompanied by the number of participants included in the analysis for that time point.

Changes in interval endpoints from pre-supplementation will be calculated as:

$$\text{Change to } V_i = \text{Value at } V_i - \text{Value at } V_{\text{pre-supplementation}}$$

P-values will be rounded to three decimal places. P-values less than 0.001 will be reported as <0.001. P-values less than or equal to 0.05 will be considered statistically significant. All analyses will be performed using R Statistical Software version 3.6.1 (R Core Team, 2019) for Microsoft Windows.

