2.4.5 Adjustments of Multiple Comparisons

Since there are only two study groups involved, there will be no pairwise comparisons requiring adjustment. There will be no adjustment for multiple outcomes.

3. Reference List

2. Mark Mather, Linda A. Jacobsen, Kelvin M. Pollard. Aging Baby Boomers to Face Caregiving, Obesity, Inequality Challenges [Internet]. population reference bureau; 2016 Jan. Available from: <https://www.prb.org/unitedstates-population-bulletin/>
3. Diabetes [Internet]. world health organization; 2018 Oct. Available from: <https://www.who.int/news-room/fact-sheets/detail/diabetes>
4. RiaGev® [Internet]. bioenergy life science Inc.; Available from: <http://bioenergylifescience.com/#products>
5. Compound Summary for CID 10975657 D-Ribose [Internet]. National Center for Biotechnology Information; [cited 2019 Feb 28]. Available from: <https://pubchem.ncbi.nlm.nih.gov/compound/D-ribopyranose#section=Food-Additives-and-Ingredients>
7. Niacin Fact Sheet for Health Professionals [Internet]. National Institutes of Health; 2019. Available from: <https://ods.od.nih.gov/factsheets/Niacin-HealthProfessional/#h9>

4. Appendix

Table 3. Summary of outcomes and analysis methods

Outcome	Data type	Between groups analysis methods
Primary Outcome		
1. The change in whole blood NAD+ levels from baseline to day 8 when supplemented with RiaGev™ or comparator.	Interval	Repeated-measures mixed ANCOVA
Secondary Outcomes		
1. The change in serum glucose and insulin as assessed by an Oral Glucose Tolerance Test (OGTT) at t=0, 15m, 30, 45m, 60m, 90m and 2h after a 7-day supplementation with either RiaGev™ or comparator	Interval	Repeated-measures mixed ANOVA (change in concentrations); mixed ANOVA (iAUC)
2. The change in serum Glutathione/Glutathione disulfide (GSH/GSSG) ratio after a 7-day supplementation with either RiaGev™ or comparator	Interval	Repeated-measures mixed ANCOVA
3. The change in serum adenosine triphosphate/ adenosine monophosphate (ATP/AMP) ratio after a 7-day supplementation with either RiaGev™ or comparator	Interval	Repeated-measures mixed ANCOVA

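### The iAUC comparison does not say which iAUC is the response, and it omits the same-period Day 1 iAUC that the protocol's covariate rule would include

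*SAP*

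**What the plan says.** SAP 1.4 and 2.2.2 list as the first secondary outcome the change in OGTT glucose and insulin after 7 days of supplementation. SAP 2.2.2 analyses it in two ways.

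- **Concentrations.** "The change in serum glucose and insulin will be represented as change in mean concentrations at each time point". The model is a repeated-measures mixed ANOVA with treatment, time, sequence, period and random subject. Within-group tests compare Day 1 with Day 8.
- **iAUC.** "An incremental area under the curve (iAUC) will be calculated for each group and compared between groups using mixed ANOVA". The terms listed for this model are sequence, period and product group, all fixed, and a random effect for the participant. No day is named for the iAUC, and the model has neither a day term nor a Day 1 iAUC.

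SAP Table 3 attaches the word change to the concentrations and lists iAUC separately, under mixed ANOVA.

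Three other places bear on this.

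- SAP 2.1 has a general rule: "Changes in interval endpoints from pre-supplementation will be calculated as" the value at the visit minus the pre-supplementation value.
- Protocol 11.3 plans ANCOVA for continuous efficacy endpoints. The dependent variable is the measurement at each visit, and "the value at baseline (Day 1) will be the covariate".
- In SAP Table 2 the row "OGTT: glucose and insulin T= 0, 15m, 30m, 45m, 60m, 90m, 2h" is marked at Visits 2, 5, 6 and 9, which are Day 1 and Day 8 of each period.

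**The concern.** Each participant will have four iAUC values per analyte, and the SAP does not say which of them enter the model. Three analyses fit the sentence: Day 8 only, change from Day 1, or all four values together. They differ in precision, and the third would not estimate the product effect at all. An analyst could choose among them after seeing the data.

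The protocol already has a rule that would settle the matter, with the Day 1 value as covariate. The SAP's iAUC model drops it without comment. With 18 participants, a chance difference in Day 1 response between the two periods can be noticeable, and the value needed to adjust for it is collected anyway.

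**Working it through.** **Figures in the plan.** The documents give no SD, power or sample size for iAUC. The calculation behind the 18 participants (protocol 11.1) concerns NAD+, so there is no iAUC figure to reproduce.

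**Inputs**

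- From the documents: n = 18 in a two-period crossover, 9 per sequence. The 20% loss in protocol 11.1 leaves 18 × 0.8 = 14.4, so n = 14 is shown as well.
- Assumed, because the documents give neither: rw, the correlation of Day 1 and Day 8 iAUC in the same period, and rx, the correlation of any two iAUC values from different periods. Variances are taken as equal.

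**Formulas.** Take the difference between a participant's two periods, in units of the iAUC variance.

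- Day 8 only: variance 2(1 − rx).
- The covariance of the Day 8 difference with the Day 1 difference is 2(rw − rx), so their correlation is k = (rw − rx)/(1 − rx).
- Change, relative to Day 8 only: variance ratio 2(1 − k).
- Day 1 covariate, relative to Day 8 only: variance ratio 1 − k², times 1 + 1/(n − 4) for estimating the slope. The t quantile moves from n − 2 to n − 3 degrees of freedom.

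At n = 18 the small-sample penalty on CI width is √(1 + 1/14) × (2.131/2.120) = 1.04. At n = 14 it is √(1 + 1/10) × (2.201/2.179) = 1.06.

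**95% CI width relative to Day 8 iAUC alone**

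| rw / rx | k | Change in iAUC | Day 1 covariate, n=18 | Day 1 covariate, n=14 |
|---|---|---|---|---|
| equal | 0 | 1.41 | 1.04 | 1.06 |
| 0.6 / 0.5 | 0.2 | 1.27 | 1.02 | 1.04 |
| 0.7 / 0.5 | 0.4 | 1.10 | 0.95 | 0.97 |
| 0.8 / 0.5 | 0.6 | 0.89 | 0.83 | 0.85 |
| 0.9 / 0.5 | 0.8 | 0.63 | 0.62 | 0.64 |

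Example at 0.8/0.5: k = 0.3/0.5 = 0.6. Change gives √(2 × 0.4) = 0.89. The covariate gives √(1 − 0.36) × 1.04 = 0.83.

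**Break-even.** The covariate narrows the interval once k exceeds about 0.28 (n = 18) or 0.33 (n = 14). A change score needs k above 0.5. Because 1 − k² = (1 − k)(1 + k) is never more than 2(1 − k), the covariate is never less precise than the change score, apart from the small-sample penalty.

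**Chance Day 1 difference.** At rx = 0.5 and n = 18, one standard error of Day 1 imbalance between products is √(1/18) = 0.24 SD. Given such an imbalance, the Day 8-only contrast shifts by k × 0.24: about 0.05 SD at k = 0.2 and 0.14 SD at k = 0.6.

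**Both days pooled.** Products do not differ on Day 1 apart from chance and carryover, and differ by δ on Day 8. With no day term or interaction, the treatment coefficient averages the two: (0 + δ)/2 = δ/2.

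**Expectation.** In simulation (n = 18, 4,000 runs, true effect 0.5 SD, no carryover), Day 8 only, change and covariate adjustment all averaged between 0.497 and 0.505. When 25% or 50% of the effect was left in the period 2 baseline but not at Day 8 (rw/rx 0.7/0.6), the change estimate averaged 0.56 or 0.62. Covariate adjustment averaged 0.51 or 0.53, and Day 8 only stayed at 0.50.

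**The case against.** A reader might infer that the iAUC comparison fails to answer the change question, or that it is biased. The documents do not support that. The SAP never says that Day 8 iAUC is the response, and the general change rule in SAP 2.1 leaves a change in iAUC open. Even if Day 8 alone is meant, randomisation gives its contrast the same expectation as the contrast in changes when there is no carryover. A chance Day 1 difference is random error, which the standard error already reflects.

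A reader might also infer that the Day 1 curve is wasted. It is not: the concentration analysis and the within-group tests use it. Only a Day 1 iAUC term is missing.

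The strongest objection is to any claim of free precision. The random subject effect already removes between-participant variation, so a period baseline helps only if rw clearly exceeds rx. The schedule does not establish that. Visits 2 and 5 are 7 days apart, and Visits 5 and 6 are separated by a 7-day (+3) washout. At 0.6/0.5 the covariate widens the interval slightly. This objection stands, and it limits what can be claimed.

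Table 3 is weak evidence either way. It labels the other four secondary outcomes ANCOVA and this one ANOVA, but the terms that SAP 2.2.2 lists for those ANCOVA models name no baseline covariate either. Protocol 11.3 is general and does not name iAUC.

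The undefined response and the unexplained departure from the protocol's covariate rule are not answered by any of this.

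**Conclusion.** The point holds as a gap in specification with a cheap improvement attached. The iAUC response is undefined, and the same-period Day 1 iAUC is left out although it is collected and the protocol's own rule would use it.

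The possible cost of adding it is an interval about 4% wider than Day 8 alone at n = 18 (6% at n = 14). The possible gain is about 5% to 17% at same-period correlations of 0.7 to 0.8 with a cross-period correlation of 0.5. The larger risks lie in the readings that the text leaves open: up to about 41% wider for an unadjusted change, and roughly half the effect if both days are pooled without a day term.

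The sizes rest on assumed correlations with rw at least rx, equal variances and a common cross-period correlation. None of these comes from the documents. The missing definition does not depend on them. Severity is low to moderate: this is a summary measure within one secondary outcome, and the change in concentrations is analysed directly alongside it.

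**What to change.** Replace the iAUC sentence in SAP 2.2.2 so that it states:

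- **Response:** Day 8 iAUC in each period, for glucose and insulin separately.
- **Covariates:** the same-period Day 1 iAUC and the participant's mean Day 1 iAUC. With the mean in the model, the Day 1 slope is estimated from within-participant differences.
- **Other terms:** treatment, sequence, period and random subject, as now.

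Change the iAUC entry in Table 3 to match. If the sponsor prefers Day 8 iAUC without the covariate, the SAP should say so and explain the departure from protocol 11.3.

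The cost is one SAP sentence and one table entry, fixed before unblinding, with no new data. The statistical cost is about one degree of freedom and the possible 4% to 6% widening.
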